4.1.3. Multicentre Studies

Due to the small sample size of this first time in human study, if multiple centres are utilised for recruitment purposes, all data will be pooled and no summaries will be provided by site or country.

4.1.4. Model Checking Diagnostics

Model checking diagnostics for dose proportionality and dose accumulation analysis will include the following:

- The Kenward and Roger method for approximating the denominator degrees of freedom and correcting for bias in the estimated variance-covariance of the fixed effects will be used.
- An unstructured covariance structure for the R matrix will be used by specifying 'type=UN' on the REPEATED line.
 - In the event that this model fails to converge, alternative correlation structures may be considered such as CSH or CS.
 - Akaike's Information Criteria (AIC) will be used to assist with the selection of covariance structure.
- Distributional assumptions underlying the model used for analysis will be examined by obtaining a normal probability plot of the residuals and a plot of the residuals versus the fitted values (i.e. checking the normality assumption and constant variance assumption of the model respectively) to gain confidence that the model assumptions are reasonable.

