4.3.2.1. Dose Proportionality

The following pharmacokinetic statistical analyses will only be performed if sufficient data are available (i.e. if more than 5 subjects have well defined plasma profiles). If the dose with limited data is at the lower end of the dose range, the data will be excluded and the appropriate analysis conducted on the rest of the data. However if there are non-calculable PK parameter data at intermittent doses no statistical analyses will be performed. A minimum of 3 doses will be required to assess dose proportionality. The assessment of dose proportionality will utilise Part A data only.

Dose proportionality will be assessed using the following two methods:

Pharmacokinetic Statistical Analyses for Dose Proportionality: Power Method	
Endpoint(s)	
• AUC(0-Inf) (if determined, otherwise use AUC(0-t)), Cmax	• Each endpoint to be assessed separately.
Model Specification	
• $\log_e(Y) = \beta \times \log_e(\text{dose}) + \log_e(\alpha)$ where Y is the pharmacokinetic parameter and $\log_e(\alpha)$ is an intercept term.	
Model Results Presentation	
• The coefficient of the slope with 90% confidence intervals, on the log scale, will be calculated, using the pooled estimate of variance, and used to assess dose proportionality.	• Point estimates and confidence intervals for the slope will be reported to 2 decimal places

Pharmacokinetic Statistical Analyses for Dose Proportionality: ANOVA Method	
Endpoint(s)	
• AUC(0-Inf) (if determined, otherwise use AUC(0-t')), Cmax	• Each endpoint to be assessed separately.
Model Specification	
• The PK parameter will be dose-normalised prior to loge-transformation by multiplying by reference dose / dose	• Dose will be fitted as a fixed effect, subject as a random effect using DDFM=KR.
• Separate lines will be fitted for each cohort by including terms for cohort and cohort*log _e (dose). If the slopes are not significantly (p-value<0.05) different from each other, the interaction term will be removed and a single slope estimate obtained. If the slopes are significantly different from each other, a separate slope estimate and associated 90% confidence interval will be reported for each cohort.	• The reference dose will be chosen based on the lowest clinically relevant dose over which PK can be adequately described, with each other dose as the test doses in the construction of the ratio $\mu(\text{test})/\mu(\text{reference})$.
Model Results Presentation	

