4.3.2.2. Accumulation and Steady State Assessment

The assessment of accumulation and steady state will be performed following repeated dosing of GSK3923868 in Parts B and C only.

Pharmacokinetic Statistical Analyses	
Endpoint(s)	
•	Accumulation: AUC(0-τ), Cτ (if data permit), Cmax on Day 14 (Part B), Day 7 (Part C) compared to Day 1
•	Steady State: Cτ from Day 1 to Day 14 (Part B) or Day 7 (Part C)
•	Each endpoint to be assessed separately following a log-transformation.
Model Specification	
•	A mixed effect model will be fitted with day as a fixed effect and subject as a random effect.
•	The Kenward & Roger (KR) degrees of freedom approach will be used.
•	Day 14 will be compared to Day 1 in order to estimate the accumulation ratio(s)
•	The accumulation ratio(s) and 90% confidence interval will be calculated by back-transforming the difference between the least square means for the two days and associated 90% confidence interval.
Model Results Presentation	
•	Point estimates and confidence intervals for the ratios will be reported to 2 decimal places
•	Scatter plots of each endpoint against day will be produced. The data points for each subject will be joined with straight lines
•	Boxplots of each endpoint against day will be produced. Each treatment will be put on a separate page.

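### An unstructured R matrix on top of a random subject effect is redundant and, if indexed by dose or study period in Part A, has no valid fit for dose proportionality

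*SAP*

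**What the plan says.** SAP 4.1.4 opens its list with "Model checking diagnostics for dose proportionality and dose accumulation analysis will include the following". Under it:

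- Default: "An unstructured covariance structure for the R matrix will be used by specifying 'type=UN' on the REPEATED line".
- Fallback: "In the event that this model fails to converge, alternative correlation structures may be considered such as CSH or CS".
- Choice: "Akaike's Information Criteria (AIC) will be used to assist with the selection of covariance structure".

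The model sections then add a subject effect. SAP 4.3.2.1 (ANOVA method): "Dose will be fitted as a fixed effect, subject as a random effect using DDFM=KR". SAP 4.3.2.2 (accumulation and steady state): "A mixed effect model will be fitted with day as a fixed effect and subject as a random effect".

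SAP 4.3.2.1 also describes the variance behind each interval. For the power model, the slope interval "will be calculated, using the pooled estimate of variance, and used to assess dose proportionality", and no subject term is stated. For the ANOVA, the 90% interval is to rest on the residual variance.

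No section says what the repeated effect is: dose, treatment period, or order within cohort.

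**The concern.** A random subject intercept adds a constant to every element of a participant's covariance matrix. An unstructured matrix plus a constant is still unstructured, so the two terms cannot be separated. That alone is untidy and not damaging. The harm arises where the design cannot support an unstructured matrix at all.

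Part A pools two cohorts that share no participants, and most participants have only two active doses. If the default has no valid fit there, the reported 90% intervals for the dose ratios depend on where the optimiser stops or on an unordered fallback. That fallback is tied only to non-convergence. The pooled-variance and residual-variance wording also implies a single common variance, which an unstructured matrix does not have. Two programmers could both follow this SAP and report different intervals.

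**Working it through.** **Inputs.** Six Part A doses: 50, 100 and 250 mcg in Cohort 1; 500, 1000 and 3000 mcg in Cohort 2 (Protocol 6.1). Cohorts combined for PK (SAP 4.3). No participant joins two cohorts (Protocol 4.1). In each cohort of 12, 3 receive active in all periods and 9 in two (Protocol 4.1, Table 2). Active participants: 9 per Part A dose, and 12 in each of Parts B and C (SAP 5). The SAP gives no figure for the covariance model. The count of 9 per dose is reproduced from Table 2: (3×3 + 9×2)/3 = 27/3 = 9.

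**Redundancy.** An unstructured matrix over K points has K(K+1)/2 parameters. Adding a subject variance adds a parameter but no rank:

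- K = 2: 4 parameters, rank 3.
- K = 7: 29 parameters, rank 28.
- K = 14: 106 parameters, rank 105.

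The fallback has the same flaw. CS plus random subject has 3 parameters and rank 2. CSH plus random subject is identifiable for three or more points, but for two points has 4 parameters and rank 3.

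**Part A, R indexed by dose or by periods 1 to 6.**

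1. K = 6 gives 21 parameters: 6 variances and 15 covariances. Within-cohort covariances number 3 + 3 = 6. The other 9 link doses in different cohorts and are never observed in one participant. Identifiable: 6 + 6 = 12 of 21, or 12 of 22 with the subject effect.
2. The 9 unobserved covariances enter no participant's own matrix, so by themselves they change no interval. The two 3×3 within-cohort blocks matter. Each covariance in them rests on 6 participants (3 complete, 3 from one two-dose sequence).
3. Take the direction perpendicular to the differences among the 3 complete participants' log PK vectors, and let the variance λ in that direction shrink. The three log-determinants add 3 × ½ × ln(1/λ). The REML fixed-effect term takes back ½ × ln(1/λ). The fitted means can move so that these three participants have no residual in that direction, and the two-dose participants keep non-singular 2×2 matrices. The net gain is ln(1/λ), without bound.
4. Numerical check in one simulated data set: the REML log-likelihood rose from 32.4 at λ = 1e-4 to 46.2 at λ = 1e-10. The gain is 13.8, and ln(10⁶) = 13.8.
5. If low doses are dropped for limited data, as SAP 4.3.2.1 allows, the Cohort 2 block still has only 3 complete participants and the same problem.

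**What an optimiser reports.** In 100 simulated pooled Part A data sets (assumed log-scale SDs 0.40 between and 0.25 within subjects), 32 fits ran to a singular matrix and 68 stopped at an interior point. In a one-cohort simulation (300 runs, same SDs, t on 13 df, no Kenward-Roger adjustment), 75 fits were singular. Nominal 90% intervals covered about 80% under the unstructured matrix and 88% under a random intercept.

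**Part A, R indexed by order within cohort.** One 3×3 matrix common to both cohorts has 6 parameters and rank 6, with 0 of 100 singular fits. This reading is estimable.

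**Repeat dosing, 12 active participants.** With one mean per day, the residual covariance has rank at most 12 − 1 = 11.

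- Two-day accumulation: 3 parameters, estimable; it is a paired comparison.
- Part C troughs, 7 days: 28 parameters, rank 7 of 7, estimable.
- Part B troughs, 14 days if daily: 105 parameters, rank 11 of 14, not estimable. Failure begins at 12 time points.

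**The case against.** The strongest reply is that the default works for several of its uses: two-day accumulation, Part C troughs, and Part A if R is indexed by order within cohort. SAP 4.1.4 does not name the steady-state analysis, and SAP 4.3.2.2 describes an interval only for accumulation ratios. Daily Part B troughs are an assumption, because the schedule row is broken in the text available. CSH and CS are named in advance. The residual-variance and pooled-variance wording already points to the simple model. All of this stands, and it sets the limits of the point.

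It does not remove the problem. The SAP never says order within cohort is the index. Dose is the natural reading for a dose ANOVA, and the SAP numbers the Part A periods 1 to 6. SAP 4.3.2.2 gives one model for accumulation and steady state, so a programmer has no other covariance rule for troughs.

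Stronger readings that a reader might infer are not supported:

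- That the planned model cannot be run for most of its uses. This holds only for Part A under dose or period indexing, and for Part B troughs at 12 or more time points.
- That the structure is picked to suit the results. The stated trigger is non-convergence, and AIC only assists.
- That choosing CSH over CS materially changes coverage. One simulation gave 86% against 90%, another 84.7% against 85.0%, with Monte Carlo error of about 2 points. No weight is placed on this.
- That a random intercept should be imposed everywhere. For last against first trough with AR(1) errors (assumed rho 0.5 to 0.9), its 90% interval is 14% to 34% narrower than the paired one. Its coverage was 84% (7 days) and 87% (14 days) at rho 0.5, and 76% for both at rho 0.9, against about 90% for the paired comparison.

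**Conclusion.** The point holds in limited form. Unstructured R plus random subject is redundant wherever both are stated; for two-day accumulation and Part C troughs this is harmless. For the pooled Part A ANOVA indexed by dose or by periods 1 to 6, 12 of 21 parameters are identifiable and the REML likelihood has no maximum. Any fit reported as converged is a local optimum, and its 90% intervals are likely too narrow (about 80% coverage in the one-cohort simulation). For Part B troughs the default fails only if there are 12 or more time points and SAP 4.1.4 is taken to apply.

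Assumptions: complete data, no replacements, and the stated SDs. The SAS procedure itself was not run, and Kenward-Roger adjustment was not applied in the coverage simulation, so the identifiability and likelihood results are firmer than the coverage figures. The power model states no subject effect, so the redundancy is not written for it, although SAP 4.1.4 still covers it.

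No hypothesis is tested on these estimates. They are secondary, descriptive PK results, and the primary safety endpoints are unaffected.

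**What to change.** - **Part A dose-proportionality ANOVA and two-day accumulation.** Remove the type=UN, fallback and AIC bullets. Specify subject as a random intercept, one residual variance and Kenward-Roger degrees of freedom. This agrees with the variance wording already in SAP 4.3.2.1. With complete data, the two-day ratio equals the back-transformed paired log difference.
- **Power model.** State whether subject is included, so that the pooled variance has a defined meaning once the unstructured default is gone.
- **Steady-state troughs.** State that a covariance rule applies, and name the repeated effect. Use either random subject or a prespecified low-parameter structured R, not an unstructured one and not both, with a fixed fallback order. Do not impose a random intercept alone, because serial correlation between days would make its intervals too narrow.

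The cost is SAP wording only. Design, sampling and conduct do not change.

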4.2. Primary Endpoints Analyses

The safety analyses will be based on the Safety Analysis Set, unless otherwise specified.

Primary Endpoints:

- Adverse events (AEs) and serious adverse events (SAEs).
- Clinically significant laboratory values, vital signs, 12-lead electrocardiogram (ECG) and spirometry measurements up to Day 2 of the final treatment period in Part A, and Day 18 in Part B.
- Clinically significant laboratory values, vital signs, 12-lead ECG and spirometry measurements up to Day 8 in Part C.

4.2.1. Definition of endpoints

Adverse events will be coded using the standard Medical Dictionary for Regulatory Affairs (MedDRA dictionary).

Grade 1 AEs are defined as mild. Grade 2 or higher AEs are defined as moderate or severe. This study will report AEs as mild, moderate or severe.

A study intervention-related AE/SAE is defined as an AE/SAE for which the investigator classifies the possible relationship to study intervention as "Yes". A worst-case scenario approach will be taken to handle missing relatedness data, i.e. the summary table will include events with the relationship to study intervention as 'Yes' or missing.

Spirometry assessments are performed in triplicate with the highest value reported.

Clinically significant values are defined as:

- Values in the potential clinical interest (PCI) ranges for laboratory values, vital signs and ECGs
- Values that achieve the study stopping criteria (protocol section 7.2.5) for spirometry

The same PCI ranges will be used for both healthy volunteers and stable asthmatics, with all ranges being defined in the OPS.

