**cci**

CCI

In both cohorts of Part B, participants will be administered treatment for 14 days. The treatment duration will ensure a thorough assessment of safety and tolerability in the lung (target organ) and aligns with the proposed treatment duration in future patient studies.

Part C will progress once the results from Part B has been reviewed. Part C is considered necessary to inform on the early safety and tolerability profile of GSK3923868 in stable asthmatics before progression to efficacy studies where asthmatics will receive GSK3923868 on a background of HRV infection. Part C will recruit two strata of asthmatics: 1) SABA and/or intermittent ICS/LABA users who are the primary population of interest in early clinical trials, and 2) Regular ICS or ICS/LABA users to support future clinical studies and assess overall safety in treated asthma.

CCI

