### 7.2.5. Spirometry Stopping Criteria

Any participant experiencing a reduction in FEV1 at the 1-hour post-dose time point compared to daily predose value of > 25% in Parts A and B and > 20% in Part C will be withdrawn from the study.

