**9.4.1.2. Laboratory values, vital signs, 12-lead electrocardiogram and Spirometry**

Whilst all data collected will be summarized, only measurements which are clinically significant at any timepoint between randomisation and follow up will be reported as part of the primary endpoint. Potential clinical interest (PCI) ranges will be defined in the SAP.

This data includes:

- Laboratory results for haematology, clinical chemistry and urinalysis (see [Appendix 2](#) for full details).
- Vital Signs measurements for semi supine systolic and diastolic blood pressure, pulse rate, respiratory rate and temperature
- 12-lead safety electrocardiogram (ECG) measurements for heart rate, PR, QRS, QT and QT interval corrected for heart rate according to Frederica's formula (QTcF) intervals
- Spirometry measurements for FEV1 and FVC

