4.2.2.2. Laboratory Data, Vital Signs, ECGs and Spirometry

For laboratory data, separate tables for haematology, clinical chemistry and urinalysis tests will be produced. Liver biochemical parameters will be included with clinical chemistry tests. Vital signs data will include semi supine systolic and diastolic blood pressure, pulse rate, respiratory rate and temperature measurements.

ECG data will include PR, QRS, QT and QTcF intervals.

Spirometry data will include FEV₁ and FVC measurements.

For haematology, clinical chemistry, urinalysis, vital signs, ECG and spirometry data the following information will be summarised:

1. Clinically significant values at each visit
2. Raw and change from baseline values at each visit

Note: The first table is the only one included as part of the primary endpoint. [redacted]

[redacted]

In order to detect potential bronchospasms, an additional table for spirometry values will be produced which summarises the changes between daily pre- and post-dose FEV₁ and FVC values.

For ECGs, a figure plotting the baseline QTcF and the worst-case post-baseline values will be produced. The figure will have reference lines at 480 and 500 msec for both the ordinate and the abscissa axes. There will be diagonal reference lines at equality (i.e. a 45 degree line), at equality plus 30 msec, and at equality plus 60 msec.

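### The primary spirometry table counts only within-day FEV1 falls, so a decline that builds up between days, the Part C Day 8 reading and all FVC values cannot register in it

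*SAP*

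**What the plan says.** SAP 4.2.1 gives two routes to a clinically significant value. The first is "Values in the potential clinical interest (PCI) ranges for laboratory values, vital signs and ECGs"; spirometry is not in that list. The second is "Values that achieve the study stopping criteria (protocol section 7.2.5) for spirometry".

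The Protocol 7.2.5 criterion is: "reduction in FEV1 at the 1-hour post-dose time point compared to daily predose value of > 25% in Parts A and B". The Part C limit is a fall of more than 20%. The criterion names FEV1 only, and its reference is the same day's predose reading.

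SAP 4.2.2.2 then plans, for FEV1 and FVC, a table of clinically significant values and a table of raw values and changes from baseline. It adds: "Note: The first table is the only one included as part of the primary endpoint". A further spirometry table of daily pre-to-post changes is meant to pick up bronchospasm.

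Four other statements matter here:
- SAP 4.2 runs the spirometry endpoint to Day 18 in Part B and Day 8 in Part C.
- Protocol 9.4.1.2 lists both FEV1 and FVC among the primary endpoint data.
- SAP 4.1.2 sets one baseline for all endpoints, the last non-missing value before the first dose (per treatment period in Part A).
- Protocol 4.2 says of the 14 days of dosing in Part B: "The treatment duration will ensure a thorough assessment of safety and tolerability in the lung (target organ".

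**The concern.** A same-day reference suits acute bronchospasm after a single dose. What Parts B and C add is 14 and 7 days of dosing, and with it the question of whether airway effects accumulate. Protocol 2.3.1 names respiratory tract irritancy as a risk on the strength of a 4-week inhaled rat study, and lists spirometry as part of the monitoring.

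If predose FEV1 drifts down over days, the reference drifts with it. The primary spirometry table could then show no events in participants whose lung function is well below where it started. The plan judges other measures against a fixed starting point in repeat dosing: QTcF change against Day 1 predose (Protocol 7.2.4) and peak flow against Day 1 predose (Protocol 7.2.6). The spirometry event does not use the SAP's own fixed baseline.

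**Working it through.** **Which readings can be events.** Under Protocol 7.2.5 an event needs a post-dose FEV1 and a predose FEV1 from the same day.

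- Predose FEV1: serves only as the reference, so it cannot be an event.
- Part C Day 8: spirometry is scheduled, but the last dose is on Day 7, so Day 8 has no predose value. It cannot be an event, although the endpoint runs to Day 8.
- FVC: 7.2.5 gives it no criterion, so it cannot be an event.
- Post-dose FEV1: can be an event, but only for the part of the decline that occurs within that day.

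**The plan's only operating figure.** SAP section 5 gives the chance of seeing no event among 12 active participants as 54% at a true rate of 5% and 7% at 20%. With P(no event) = (1 − p)^12:
- 0.95^12 = 0.540
- 0.80^12 = 0.069

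Both reproduce. For a decline that is purely between days, the primary spirometry table shows no event with probability 100% at any true rate. If such declines were countable, the plan's 54% and 7% would apply.

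**Illustration.** The documents give no drift rate, so the rates are assumptions, shown over a range. Let predose FEV1 fall by a fraction g per day, with no additional within-day fall. On day d it is 1 − (1 − g)^(d−1) below Day 1. The 20% and 25% of Protocol 7.2.5 serve here as a yardstick against Day 1, not as proposed clinical limits.

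| Assumed g per day | Part C, Day 7 below Day 1 | First day more than 20% below | Part B, Day 14 below Day 1 | First day more than 25% below | Events under 7.2.5 |
|---|---|---|---|---|---|
| 2% | 1 − 0.98^6 = 11.4% | none by Day 7 | 1 − 0.98^13 = 23.1% | none by Day 14 | 0 |
| 3% | 1 − 0.97^6 = 16.7% | none by Day 7 | 1 − 0.97^13 = 32.7% | Day 11 | 0 |
| 4% | 1 − 0.96^6 = 21.7% | Day 7 | 1 − 0.96^13 = 41.2% | Day 9 | 0 |
| 5% | 1 − 0.95^6 = 26.5% | Day 6 | 1 − 0.95^13 = 48.7% | Day 7 | 0 |

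The zeros hold as long as no within-day fall exceeds the threshold; adding a constant within-day fall of 5% or 10% to the 2%, 3% and 5% rates still gives zero. A mixed case: a Part C participant who is 20% below Day 1 at predose and then loses 19% after dosing is 1 − 0.80 × 0.81 = 35.2% below Day 1, and is not counted.

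**A neighbouring mismatch.** Protocol 7.2.5 uses a 1-hour reading, while the Part C schedule has spirometry at predose and 30 minutes only. Read literally, no Part C value meets the definition. These passages must be reconciled, but aligning the clock times would not change the daily reference.

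**The case against.** A reader might infer that the primary endpoint as a whole cannot register a cumulative decline, or that participants could lose lung function steadily behind a clean report. The documents do not support that.

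- Adverse events are the first component of the primary endpoint, and Protocol 10.3.1 includes safety assessments that worsen from baseline when the investigator judges them clinically significant.
- The change-from-baseline table carries minimum and maximum (SAP 4.1.1), so with 12 active participants per part the worst individual is visible.
- In Part C, Protocol 7.2.6 uses peak flow against Day 1 predose, measured twice daily.
- No hypothesis is tested, so calling a table primary changes no error rate.

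All of this stands, and it confines the point to the spirometry table. It does not remove it. The adverse event route depends on judgement, and in Part C findings tied to the underlying disease are excluded unless more severe than expected. A minimum does not say how many participants declined. The peak-flow rule measures something other than FEV1, needs progressive symptoms and at least 3 sustained days, and does not apply to Part B.

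Three further cautions also stand. The percentages in 7.2.5 were set for an acute FEV1 fall, and nothing in the documents supports them for multi-day change or for FVC. The Part B spirometry row in the schedule is not legible enough in the available text to confirm its days. Text after the note in SAP 4.2.2.2 is redacted, so something relevant may stand there.

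**Conclusion.** The point holds for the spirometry component of the primary endpoint. As defined, that component counts only a within-day FEV1 fall. A between-day decline, predose readings, the Part C Day 8 reading and FVC are outside it unless a single within-day FEV1 fall also crosses the threshold. This is a stated rule that misclassifies readings the endpoint is said to cover, not merely a missing detail.

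For a purely between-day decline the table is empty with certainty. How large an uncounted decline might be rests on the assumed 2% to 5% per day and on no within-day fall above the threshold. The steeper Part B figures are arithmetic limits, not predictions. The conclusion is firmest for Part C, where spirometry is scheduled on Days 1 to 8. In Part B the definition has the same gap, but how many readings it affects depends on schedule days that cannot be confirmed. The change should be made; its weight is moderate, because the decline can still be seen elsewhere in the report.

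**What to change.** In SAP 4.2.1, and in the primary table of SAP 4.2.2.2, add a row reported separately from the within-day fall. It counts participants with any scheduled FEV1 or FVC (predose, post-dose or off-dose) below the SAP 4.1.2 baseline by more than a prespecified reporting percentage. The sponsor should set that percentage for each measure before unblinding. The 7.2.5 figures can serve as a default reporting flag only. Apply the row in Part C on Days 1 to 8, and in Part B on whatever days its schedule provides.

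Leave the 7.2.5 withdrawal rule unchanged. Ask the sponsor to reconcile its daily reference with the repeat-dose objective, and its 1-hour time point with the Part C schedule.

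The cost is a few lines of SAP text and one row per table. Part C needs no new data; for Part B that depends on the schedule. Day-to-day variability, especially in asthma, will flag a few extra values, but these are expected in both arms and the placebo column puts them in context.
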